### ***Analysis of pre-treatment and post-treatment adverse events***

- All pre-treatment AEs by primary SOC and PT, showing the number (%) of patients with at least 1 pre-treatment AE, sorted by the internationally agreed SOC order and decreasing incidence of PTs within each SOC.
- All pre-treatment serious adverse events by primary SOC and PT, showing the number (%) of patients with at least 1 pretreatment serious adverse event, sorted by the internationally agreed SOC order and decreasing incidence of PTs within each SOC.
- All post-treatment AEs by primary SOC and PT, showing the number (%) of patients with at least 1 post-treatment AE, sorted by the internationally agreed SOC order and decreasing incidence of PTs within each SOC.
- All post-treatment SAEs by primary SOC and PT, showing the number (%) of patients with at least 1 post-treatment SAE, sorted by the internationally agreed SOC order and decreasing incidence of PTs within each SOC.

#### **2.4.5.2 Deaths**

An overview of Grade 5 AEs will be provided summarizing number (%) of patients with any:

- Grade 5 AE (TEAE and post-treatment).
- Fatal TEAE (regardless date of death/period).
  - Grade 5 TEAE with a fatal outcome during the treatment period,
  - Any Grade TEAE with a fatal outcome during the post-treatment period.
- Post-treatment Grade 5 AE (excluding a TEAE that worsened to Grade 5 during the post-treatment period).

The following summaries of deaths will be generated for the safety population.

- Number (%) of patients who died by study period (on-treatment, post-treatment, within 60 days of first dose) and reasons for death (disease progression, AE, other) by treatment received.
- Listing of deaths in non-randomized patients or randomized but not treated patients (this listing will be generated on the screened patients).
- All TEAEs leading to death by primary SOC and PT, sorted by the internationally agreed SOC order and by decreasing incidence of PTs.
- All TEAEs related to treatment and leading to death by primary SOC and PT sorted by the internationally agreed SOC order and by decreasing incidence of PTs.
- Number (%) of patients with TEAE(s) leading to death regardless of relationship and related to IMP by Primary SOC, HLGT, HLT and PT.
- Summary of AEs leading to death, by Primary SOC and PT
  - In context of disease progression (death within 30 days from last study treatment administration and the cause of death is disease progression),

- In context other than disease progression (death within 30 days from last study treatment administration and for whom cause of death is not disease progression or the death occurred more than 30 days from last study treatment administration and the cause of death is adverse event).

### **2.4.5.3 Analyses of laboratory variables**

Hematological and clinical biochemistry toxicities will be assessed from laboratory test parameters. Each test result will be graded by NCI-CTCAE version 4.03, whenever applicable.

For hematological parameters and for some selected biochemistry parameters, sanofi sponsor generic ranges (LLN, ULN) are defined and will be used for grading (see list of parameters in [Appendix C](#)). For other biochemistry parameters (eg, for hepatic enzymes ALT, AST, Alkaline phosphatase, total bilirubin), grading will be derived using local laboratory normal ranges.

The number of patients with abnormal laboratory tests at baseline will be presented by grade and all grades together. The frequency of patients in each grade and all grades of laboratory abnormalities during treatment will be summarized. For patients with multiple occurrences of the same laboratory variable during the treatment, the maximum grade (worst) per patient will be used.

The denominator used for percentage calculation is the number of patients with at least 1 evaluation of the laboratory test during the considered observation period.

When appropriate, the summary table will present the frequency of patients with any grade of abnormal laboratory tests and with Grade 3-4 abnormal laboratory tests.

For laboratory tests for which NCI-CTCAE V4.03 scale is not applicable, potentially clinically significant abnormalities (PCSA) values are defined as abnormal values considered medically important by the Sponsor according to predefined criteria/thresholds based on literature review. PCSA criteria will determine which patients had at least 1 PCSA during the on-treatment period, taking into account all evaluations performed during the on-treatment period, including nonscheduled or repeated evaluations. The incidence of PCSA any time during the on-treatment period will be summarized by treatment group irrespective of the baseline level.

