11.4.3.4 Other safety evaluations

Laboratory data

Clinical laboratory values will be analyzed after conversion into standard international units. International units will be used in all listings and tables. Complete blood count and serum chemistry results will be graded according to NCI-CTCAE Version 4.03, when applicable. For patients with multiple occurrences of the same laboratory variable during the TEAE period, the maximum grade (worst) per patient will be used. The denominator used for percentage calculation is the number of patients with at least 1 evaluation of the laboratory test during the considered observation period.

The number and proportion of patients with abnormal laboratory tests at baseline (ie, last assessment before the first dose of study treatments administration) will be presented for \geq Grade 3, all grades together and Grade 3 and Grade 4 separately. Similar tables showing abnormalities during the TEAE period will be provided.

When the NCI-CTCAE V4.03 scale is not applicable, the number of patients with a laboratory abnormality out-of-normal laboratory range value will be displayed.

Vital signs

Potentially clinically significant abnormality (PCSA) values are defined as abnormal values considered medically important by the Sponsor according to predefined criteria/thresholds based on literature review. The incidence of PCSAs prior to study treatment administration at any cycle during the TEAE period (on-treatment PCSAs) will be summarized by treatment group whatever the baseline level and/or according to the following baseline categories:

- Normal/missing.
- Abnormal according to PCSA criterion or criteria.

The incidence of PCSA during and after study treatment administration at any cycle during the TEAE period in the IPd arm will also be summarized.

Other evaluations

Cytokines (TNF- α , IL-1- β , IL-4, IL-6, IFN- γ), markers of complement activation (C3a, C4, CH50), serum tryptase will be summarized with descriptive statistics.

Number (%) of patients with second primary malignancies will be summarized.

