### **2.4.5.4 Analyses of vital sign variables**

A shift table of baseline ECOG PS versus best and worst ECOG PS on treatment will be provided.

For blood pressure/heart rate parameters, potentially clinically significant abnormality (PCSA) values are defined as abnormal values considered medically important by the Sponsor according to predefined criteria/thresholds based on literature review.

The incidence of PCSAs prior to study treatment administration at any cycle during the TEAE period will be summarized by treatment group whatever the baseline level and/or according to the following baseline categories:

- Normal/missing.
- Abnormal according to PCSA criterion or criteria.

The incidence of PCSA during and after study treatment administration at any cycle during the TEAE period in the IPd arm will also be summarized.

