### CRITERIA for POTENTIALLY CLINICALLY SIGNIFICANT ABNORMALITIES

---

Parameter	PCSA	Comments
Vital signs		
HR	≤50 bpm and decrease from baseline ≥20 bpm ≥120 bpm and increase from baseline ≥20 bpm	To be applied for all positions (including missing) except STANDING.
SBP	≤95 mmHg and decrease from baseline ≥20mmHg ≥160 mmHg and increase from baseline ≥20 mmHg	To be applied for all positions (including missing) except STANDING.
DBP	≤45 mmHg and decrease from baseline ≥10 mmHg ≥110 mmHg and increase from baseline ≥10 mmHg	To be applied for all positions (including missing) except STANDING.
Orthostatic Hypotension		
Orthostatic SDB	≤-20 mmHg	
Orthostatic DBP	≤-10 mmHg	
Weight	≥5% increase from baseline ≥5% decrease from baseline	FDA Feb 2007.

---

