**Table 11 - Generic ranges for hematological parameters**

LBTESTCD	LBTEST	GENDER	LBSTRESU	LBGNNRLO
HGB	Hemoglobin	F	g/L	120
HGB	Hemoglobin	M	g/L	135
LYM	Lymphocytes		10  /L	1
NEUT	Neutrophils		10  /L	1,8
PLAT	Platelets		10  /L	150
WBC	Leukocytes		10  /L	4,5
EOS	Eosinophils		10  /L	0
BASO	Basophils		10  /L	0
MONO	Monocytes		10  /L	0,18
HCT	Hematocrit	M	%	0,41
HCT	Hematocrit	F	%	0,36
RBC	Erythrocytes	F	10  /L	4
RBC	Erythrocytes	M	10  /L	4,5
INR	INR		Ratio	0.8

Based on NEJM (N Engl J Med 2004;351:1548-63.): “Laboratory Reference Values”, [name]., Ph.D., M.P.H., [name]., M.P.H., [name]., and [name].

The current list of generic ranges for biochemistry parameters (for adults) is provided in the table below:

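### SAP rules for abnormal safety values: the abnormal-baseline vital-sign category cannot be filled as written, raised INR has no limit, and laboratory tests without a CTCAE scale have no stated threshold

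*SAP*

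**What the plan says.** **Vital signs.** SAP 2.4.5.4 reports on-treatment PCSAs for heart rate and blood pressure overall and/or by two baseline categories: Normal/missing, and "Abnormal according to PCSA criterion or criteria". The criteria are in SAP Appendix A. Heart rate, for example, is a PCSA if "≤50 bpm and decrease from baseline ≥20 bpm" or "≥120 bpm and increase from baseline ≥20 bpm". The systolic and diastolic rows have the same two-part form. Protocol 11.4.3.4 uses the same two baseline categories.

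**Graded laboratory tests.** For hematology and selected biochemistry, SAP 2.4.5.3 says that "sanofi sponsor generic ranges (LLN, ULN) are defined and will be used for grading", and refers to Appendix C. Local laboratory ranges are provided for the remaining biochemistry parameters only. In Appendix C, Table 11 ("Generic ranges for hematological parameters") has a single limit column, whose header is the lower-limit code. The header of Table 12, for biochemistry, shows both limits.

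**Laboratory tests without a CTCAE scale.** SAP 2.4.5.3 says that "PCSA criteria will determine which patients had at least 1 PCSA during the on-treatment period", with PCSAs defined "according to predefined criteria/thresholds based on literature review". For the same tests, Protocol 11.4.3.4 says that "the number of patients with a laboratory abnormality out-of-normal laboratory range value will be displayed".

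**The concern.** Each rule should let a programmer derive a table from the SAP alone.

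- The baseline split is meant to separate patients who were already abnormal from those who became so on treatment. If no baseline can be classed as abnormal, the split does nothing.
- For INR the direction of interest is upward, and that is the side with no limit.
- For tests without a CTCAE scale, a workable protocol rule has been replaced by one whose thresholds are not printed. The limits would then have to be chosen or found later, in an open-label trial with data in hand.

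At stake are the accuracy and reproducibility of between-arm safety summaries. No efficacy test, alpha level or sample size depends on any of this.

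**Working it through.** The plan states no result here to reproduce. The check is of the rules themselves.

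**1. Baseline category (SAP 2.1.1, 2.4.5.4, Appendix A).** Baseline is one value per patient, the last up to first dose. At baseline, change = baseline − baseline = 0. Each full criterion was applied with the value set equal to baseline, for every integer from 20 to 260 (260 − 20 + 1 = 241 values).

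| Parameter | Absolute part | Required change | Change at baseline | Values meeting the full criterion |
|---|---|---|---|---|
| Heart rate | ≤50 or ≥120 bpm | ≥20 bpm | 0 | 0 of 241 |
| Systolic BP | ≤95 or ≥160 mmHg | ≥20 mmHg | 0 | 0 of 241 |
| Diastolic BP | ≤45 or ≥110 mmHg | ≥10 mmHg | 0 | 0 of 241 |

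Example: a baseline systolic pressure of 170 mmHg meets the absolute part (170 ≥ 160) but not the change part (0 < 20), so it goes to Normal/missing. A patient with no baseline cannot meet a change criterion on treatment either, yet is counted in that same row. With the absolute part alone the category can be filled: for heart rate, 31 integers (20 to 50) plus 141 (120 to 260) = 172 of 241 qualify.

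The orthostatic rows of Appendix A carry no change condition, but SAP 2.1.4.4 lists no orthostatic measurement among the vital signs.

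**2. Upper limits for hematology (SAP 2.1.4.3, 2.4.5.3, Table 11).** Table 11 has 14 rows, and 0 of 14 show an upper limit. INR has 0.8 only. SAP 2.1.4.3 puts INR, prothrombin time and aPTT under hematology, so the local-range provision for other biochemistry parameters does not reach them. Prothrombin time and aPTT have no row.

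**3. Tests without a CTCAE scale.** Appendix A, the only PCSA table in the SAP, covers heart rate, blood pressure, orthostatic pressure and weight; it has 0 laboratory rows. SAP 1.5 lists two changes from the protocol (removal of the PRO population flag, addition of a biomarker population). The history in SAP 1.6 does not mention this switch either.

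**4. Hematocrit unit (Table 11).** The printed limits are 0.41 (male) and 0.36 (female), unit %. They can be tested against the hemoglobin and red-cell limits in the same table: 135 g/L and 4.5 × 10^12/L for males, 120 g/L and 4 × 10^12/L for females.

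- Male, as a fraction: 410 mL of cells per litre; 135/410 = 0.33 g hemoglobin per mL of cells; 0.41/(4.5 × 10^12) L = 91 fL per cell.
- Male, as a percentage: 4.1 mL of cells per litre; 135/4.1 = 32.9 g per mL; 0.91 fL per cell, which is physically impossible.
- Female: 0.33 g/mL and 90 fL as a fraction; 33.3 g/mL and 0.90 fL as a percentage.

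The numbers are therefore fractions with a percentage label. The mismatch matters only if results are stored in %: 30 is not below 0.41, although 30% is below 41%.

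**The case against.** **Baseline split.** A sensible programmer would read baseline abnormality as the absolute limit, the protocol has the same wording, and the and/or makes the split optional. Even on the literal reading, the Normal/missing row reproduces the overall incidence, so the table is not empty of information. Missing baselines should be rare, since vital signs are due at screening and on Cycle 1 Day 1. SAP Table 10 schedules vital signs for the primary PFS analysis only, and SAP version 3 postdates it. All of this stands, and it limits the consequence. It does not make the written rule executable.

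**INR.** After screening, coagulation is tested only as clinically indicated (Protocol 1.2), so on-treatment data will be sparse. A column lost when the PDF was read cannot be fully excluded, although the Table 12 header kept both limits. The effect is small, but the gap remains.

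**Laboratory PCSA.** The text speaks of the sponsor's predefined thresholds and does not say that they are in Appendix A. A reader might infer that no such limits exist, or that these tables must show zero events in both arms. The documents do not support that: an unprinted threshold leaves the result undetermined, not zero.

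**Hematocrit.** A reader might infer that low hematocrit is never flagged. That would require results held in %, which no section states. SAP 2.1.4.3 converts values to standard international units, and if they are held as fractions the flags are correct.

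**Conclusion.** The point holds, at low severity, for descriptive safety tables only.

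- **Heart rate and blood pressure by baseline status:** followed literally, the abnormal stratum contains 0 patients whatever the data, and abnormal baselines are filed as Normal/missing.
- **Raised INR:** no limit is stated and no fallback applies. This assumes that a grade for a raised INR is set against an upper limit of normal; the CTCAE scale is not reproduced in the documents. The practical effect is small.
- **Tests without a CTCAE scale:** an undeclared departure from the protocol to a rule that the SAP alone does not determine. Which tests are affected also depends on the CTCAE scale.
- **Hematocrit:** most likely a unit-label slip, harmless if results are stored as fractions.

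A reader might extend this to the cytopenia results or to the analysis of thrombocytopenia with hemorrhage. The documents do not support that. Grading of anemia, neutropenia and thrombocytopenia rests on lower limits, which Table 11 supplies, and the hemorrhage analysis uses platelet grades and an adverse-event query, not INR or hematocrit.

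**What to change.** 1. In SAP 2.4.5.4, define abnormal at baseline by the absolute part of each Appendix A criterion (heart rate ≤50 or ≥120 bpm, systolic ≤95 or ≥160 mmHg, diastolic ≤45 or ≥110 mmHg), and show missing baseline as its own row. Since Table 10 plans vital signs only at the primary analysis, this means rerunning or footnoting that output.
2. In SAP 2.4.5.3, grade INR, prothrombin time and aPTT against the local laboratory upper limit, as is already done for hepatic enzymes.
3. In SAP 2.4.5.3, restore the protocol rule for tests without a CTCAE scale: count patients with values outside the Appendix C range where both limits are given, otherwise outside the local range. If PCSA criteria are preferred, print the laboratory thresholds and list the change in SAP 1.5.
4. In Table 11, relabel the hematocrit unit as a fraction (L/L), or state 41% and 36%. Do this together with item 3, because the restored rule would use these limits.

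Items 2 to 4 still apply to the hematology and biochemistry tables that Table 10 plans at the second interim and final OS analyses. The cost is SAP wording, a corrected unit label and a little programming, with no new data.

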### **Anemia, thrombocytopenia and neutropenia**

Shift tables showing the number of patients in each grade at baseline by worst grade during the on-treatment period and the bone marrow involvement at baseline by worst grade during the on-treatment period will be provided.

Further analyses including summary of cycle of onset (all grades and Grade  $\geq 3$ ), duration and concomitance with other hematological abnormalities will also be provided.

### **2.4.5.4 Analyses of vital sign variables**

A shift table of baseline ECOG PS versus best and worst ECOG PS on treatment will be provided.

For blood pressure/heart rate parameters, potentially clinically significant abnormality (PCSA) values are defined as abnormal values considered medically important by the Sponsor according to predefined criteria/thresholds based on literature review.

The incidence of PCSAs prior to study treatment administration at any cycle during the TEAE period will be summarized by treatment group whatever the baseline level and/or according to the following baseline categories:

- Normal/missing.
- Abnormal according to PCSA criterion or criteria.

The incidence of PCSA during and after study treatment administration at any cycle during the TEAE period in the IPd arm will also be summarized.

#### **2.4.5.5 Analyses of electrocardiogram variables**

The incidence of patients with at least 1 abnormal ECG at any time during the TEAE period will be summarized by treatment group irrespective of the baseline level and/or according to the following baseline status categories:

- Normal/missing
- Abnormal

A listing of abnormalities and analysis of AEs in appropriate SMQs (eg, Cardiac) will be provided if relevant.

#### **2.4.5.6 Analyses of other safety endpoints**

The summary statistics (including number, mean, median, Q1, Q3, standard deviation, minimum and maximum) of baseline values, peak values, change from baseline and relative change from baseline will be calculated for Cytokines (TNF- $\alpha$ , IL-1- $\beta$ , IL-4, IL-6, IFN- $\gamma$ ), markers of complement (C3a, C4, CH50) and serum tryptase when available.

For indirect antiglobulin test (IAT), a summary of patients in experimental arm with indirect Coombs test during the on-treatment period will be provided, including number (%) of patients with:

- All tests negative
- At least one positive test

And among patients with at least one positive test during study treatment, number (%) of patients with:

- Negative indirect Coombs test at baseline
- Missing indirect Coombs test at baseline

## **2.4.6 Analyses of pharmacokinetic and pharmacodynamic variables**

The population PK of isatuximab will be characterized in the population of patients in the experimental arm, using a nonlinear mixed effect modeling approach. Both rich and sparse sampling pharmacokinetic data available from Phase 1, 2 and 3 studies will be used for the analysis. The assessment of pomalidomide, pathophysiological and demographic covariate effects on the main PK parameters will be performed. Additional details of the analysis plan and the results will be provided in a separate document. The population estimates from this analysis will provide a prior distribution from which individual Bayesian estimates of the PK parameters for each patient in this study will be derived.

Pharmacokinetic plasma concentration of isatuximab will be summarized by theoretical sampling times using descriptive statistics (such as arithmetic mean, geometric mean, median, standard deviation, standard error of the mean (SEM), coefficient of variation (CV), minimum and maximum). Accumulation ratio will be calculated with concentration at the end of infusion (CEOI) (C2D1 vs C1D1 and C4D1 vs C1D1) and  $C_{\text{trough}}$  (C2D1 vs C1D8 and C4D1 vs C1D8) and will be summarized by descriptive statistics (such as geometric mean, arithmetic mean median, standard deviation, standard error of the mean (SEM), coefficient of variation (CV), minimum and maximum).

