^b **Randomization:** To take place once the consented patient has completed all the necessary screening procedures and is deemed eligible (based on assessments including myeloma specific results from central laboratory (see footnote “z”) and hematology/biochemistry local laboratory results) for study entry by the investigator or designee. All eligible patients must be randomized by contacting the Interactive Response Technology (IRT). All efforts should be made to start treatment within 3 working days even if a maximum up to 5 working days can be allowed.

^c **Cycle:** A cycle duration is 28 days. Day 1 of Cycle 1 refers to the day the patient receives the first study treatment administration. Day 1 of each subsequent cycle corresponds to Day 29 of the previous cycle. Day 8, Day 15 and Day 22 time window at Cycle 1 is ±1 day. For subsequent cycles, Day 1 and 15 time window is ±2 days and any delay above these time windows or any omission due to AE will be documented in the electronic case report form (eCRF) (please refer to details for dose modification in [Section 8.2.3](#))

^d **Demography:** Includes age, gender, ethnicity and race. Medical/Surgical History (other than multiple myeloma): Includes relevant history of previous/associated pathologies including respiratory function history; smoking status will also be collected.

^e **Prior anti-myeloma treatment and myeloma history:** Includes date of initial diagnosis of symptomatic multiple myeloma, stage of the disease at diagnosis and at study entry, type of disease at diagnosis and at study entry (heavy and light chain component), previous anti-myeloma therapy (drug name, including transplant, start and stop dates, intent, date of progression, best response and reason for discontinuation).

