1.3 PHARMACOKINETIC/PHARMACODYNAMIC FLOW CHART

IPd arm only

Study phase	Treatment phase																		End of treatment (EOT)	Post treatment Follow-up period			
	Cycle 1						Cycle 2			Cycle 3		Cycle 4			Subsequent cycles		30 ±5 days after last study treatment	60 ±5 days after last study treatment		Monthly (±7 days) for approximately 12 months			
Day	D1			D8	D15			D22	D1			D15		D1					D15		D1	D15	
Time (decimal hours)	0h Start Infusion	EOI	EOI +1h	0h Start infusion	0h Start Infusion	EOI	0h Start Infusion	0h Start Infusion	EOI	0h Start Infusion	0h Start Infusion	0h Start Infusion	0h Start Infusion	EOI	EOI +1h	0h Start Infusion	0h Start Infusion	0h Start Infusion					
Indicative clock time	8 am	12 pm	1 pm	8 am	8 am	12 pm	8 am	8 am	12 pm	8 am	8 am	8 am	8 am	8 am	12 pm	1 pm	8 am	8 am	8 am	8 am	8 am	8 am	
Treatment																							
isatuximab (IV infusion)	X-----	---X		X	X-----	---X	X	X-----	---X	X	X	X	X	X-----	---X		X	X	X				
Pharmacokinetics ^e																							
isatuximab	P00 ^a	P01 ^b	P02 ^c	P03 ^a	P04 ^a	P05 ^b	P06 ^a	P00 ^a	P01 ^b	P02 ^a	P00 ^a	P01 ^a	P00 ^a	P01 ^b	P02 ^c	P03 ^a	P00 ^a				PF0		
Pharmacodynamics ^e																							
ADA (Immunogenicity) ^f	P00 ^a				P01 ^a			P00 ^a				P00 ^a					P00 ^a				PF0	PF1 ^d	PFX ^d

^a Sample collected (within 10 min) strictly before the start of isatuximab infusion (ie, after administration of the isatuximab premedications).

^b Sample collected just before actual end of infusion (EOI). A time window of [±10 min] around the actual end of infusion will be allowed for end of infusion sample.

^c Sample collected 1 hour [±10 min] after the actual end of infusion.

^d At 60 days, if patient is positive or inconclusive for ADA, additional ADA are required every 30 days (±7 days) until sample is negative (sample ID: PF2, PF3 etc).

^e Refer to laboratory manual for sample collection, processing and shipping.

^f The sampling times for ADA detection can be modified based on the updated knowledge of isatuximab on immunogenicity. For patients still on treatment at the time of amended protocol 07, sample is no more required.

If isatuximab is stopped prior to pomalidomide and dexamethasone, ADA will be tested on D1 of the 2 next cycles. If ADA test at the second cycle administered without isatuximab is positive or inconclusive, ADA testing will be repeated every cycle until negative.

After the PFS cut-off date, no further PK samples will be collected.

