8.2.1 Study treatments (IMP)

Study treatment is defined as isatuximab/pomalidomide/dexamethasone in IPd experimental arm and pomalidomide/dexamethasone in Pd control arm.

Patients allocated to IPd arm should routinely receive pre-medications prior to isatuximab infusion to reduce the risk and severity of infusion associated reactions (IARs) commonly observed with monoclonal antibodies. Detailed guidelines for the premedication are provided in [Section 8.2.2](#) and details for management of IARs are provided in [Section 10.6.1](#).

Pomalidomide may be taken with water and should be swallowed whole. Patients are not permitted to break, chew or open the capsules. Pomalidomide should be taken with or without food, preferably at the same time every day. Patients will be asked to maintain a diary to record the doses of pomalidomide (except those administered by the study nurse/doctor).

If a dose of pomalidomide is missed, it should be taken as soon as possible on the same day. If it is missed for the entire day, the dose should not be made up and will be considered omitted (and will not be replaced). The next scheduled dose should be taken at the next scheduled time point.

If a dose of dexamethasone is missed, it should be taken as soon as possible within the next 2 days. The dose per cycle must not exceed 160 mg (80 mg if the patient is ≥ 75 years old). Patients will be asked to maintain a diary to record the doses of dexamethasone taken orally (except those administered by the study nurse/doctor).

IPd arm (experimental arm)

Drug administration (after pre-medication as described [Section 8.2.2](#)) for patients treated with isatuximab, pomalidomide and dexamethasone combination is as follows:

- Dexamethasone 40 mg (or 20 mg if the patient is ≥ 75 years old), PO (the preferred route) or IV (if PO route cannot be used whatever the reason) on Days 1, 8, 15 and 22, between 15-30 minutes (but no longer than 60 minutes) prior to isatuximab. Dexamethasone will be administered at the beginning or at the end of the isatuximab premedications depending on the route PO or IV (see [Section 8.2.2](#)).
- Isatuximab 10 mg/kg on Days 1, 8, 15, and 22 at Cycle 1, and then 10 mg/kg on Days 1 and 15 for subsequent cycles.

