Based on updated pharmacokinetic characterization of isatuximab, the plasma half-life has been re-estimated to 28 days. As duration of contraceptive measures is required to last for 5 half-lives, a revised duration of contraceptive measures and pregnancy testing of 5 months after the last isatuximab dose is required.

Protocol amendment summary of changes table

Section # and Name	Description of Change	Brief Rationale
Tabulated clinical trial summary and Section 7.2 Exclusion criteria	E27 and E28 amended to indicate that females of child-bearing potential will be required to use contraception and to be tested for pregnancy for 3 or 5 months after discontinuation of study treatment for Pd and IPd respectively; and that male patients will be required to use contraception for 3 or 5 months after discontinuation of study treatment, for Pd and IPd respectively.	Change from 3 months due to re-estimation of isatuximab plasma half-life
Flow Chart foot note j	Amended to indicate that females of child-bearing potential will be required to be tested for pregnancy for 3 or 5 months after discontinuation of study treatment for Pd and IPd respectively.	Change from 3 months due to re-estimation of isatuximab plasma half-life
Section 8.9.4 Contraceptive measures and pregnancy counseling	Amended to indicate that females of child-bearing potential will be required to use contraception, abstain from breastfeeding or blood donation and to be tested for pregnancy for 3 or 5 months after discontinuation of study treatment for Pd and IPd respectively; and that male patients will be required to use contraception and abstain from sperm or blood donation for 3 or 5 months after discontinuation of study treatment for Pd and IPd respectively.	Change from 3 months due to re-estimation of isatuximab plasma half-life
Section 10.1.5.1 60 days visit	Amended to indicate that females of child-bearing potential will be required to be tested for pregnancy for 3 or 5 months after discontinuation of study treatment for Pd and IPd respectively.	Change from 3 months due to re-estimation of isatuximab plasma half-life
Section 10.1.5.2 Further follow-up visits	Amended to indicate that females of child-bearing potential will be required to be tested for pregnancy for 3 or 5 months after discontinuation of study treatment for Pd and IPd respectively.	Change from 3 months due to re-estimation of isatuximab plasma half-life

Amended clinical trial protocol 4 (25-OCT-2018)

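### The Cycle 4 trough accumulation ratio in SAP 2.4.6 divides a 14-day trough by a 7-day trough, so it is biased low and does not form a trend with the Cycle 2 ratio

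*SAP*

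**What the plan says.** SAP 2.4.6 plans accumulation ratios on two scales. For end-of-infusion concentration they are "C2D1 vs C1D1 and C4D1 vs C1D1"; for trough they are "C2D1 vs C1D8 and C4D1 vs C1D8". All are to be summarized descriptively. The section says nothing about a change of dosing interval between these visits and gives no adjustment for one. It also plans a population-PK analysis with individual Bayesian estimates, detailed in a separate document.

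Protocol 8.2.1 sets the schedule: "Isatuximab 10 mg/kg on Days 1, 8, 15, and 22 at Cycle 1", "and then 10 mg/kg on Days 1 and 15 for subsequent cycles". The study flow chart (Protocol 1.2, cycle footnote) adds "A cycle duration is 28 days". The PK flow chart (Protocol 1.3) takes the pre-dose samples "strictly before the start of isatuximab infusion".

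The only half-life in the two documents is in Protocol Appendix P, in the rationale for amended protocol 05 on contraception: "the plasma half-life has been re-estimated to 28 days".

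**The concern.** An accumulation ratio based on troughs compares the level at the end of a dosing interval after repeated doses with the level at the end of an equal interval after one dose. If the intervals differ, the ratio also contains the extra decline over the longer one.

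The two planned trough ratios carry the same label and the same denominator, and will probably be tabulated together. A reader would take them as accumulation at Cycle 2 and accumulation at Cycle 4 on one scale. They are not on one scale. At stake is the interpretation of one descriptive PK table; no test, alpha level, sample size or efficacy result depends on it.

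**Working it through.** The documents state no accumulation ratio, so there is no plan figure to reproduce.

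**1. Time since the previous dose.** Counting C1D1 as day 0, the doses up to C3D15 fall on days 0, 7, 14, 21, 28, 42, 56 and 70.

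| Pre-dose sample | Day | Previous dose | Interval |
|---|---|---|---|
| C1D8 | 7 | C1D1, day 0 | 7 days |
| C2D1 | 28 | C1D22, day 21 | 7 days |
| C2D15 | 42 | C2D1, day 28 | 14 days |
| C4D1 | 84 | C3D15, day 70 | 14 days |

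C2D1/C1D8 is 7 days over 7 days. C4D1/C1D8 is 14 days over 7 days.

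**2. Direction of the bias.** Let S(7) and S(14) be the levels 7 and 14 days after a single dose. The SAP ratio is C4D1/S(7); the same-interval ratio is C4D1/S(14). The SAP ratio therefore equals the same-interval ratio times S(14)/S(7). That factor is below 1 whenever concentration declines between days 7 and 14, so the direction does not depend on the model.

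**3. Size.** This step assumes a linear one-compartment model, equal doses and instantaneous input. With k = ln2/half-life, the pre-dose level is C(t) = sum of exp(-k(t - d)) over earlier doses d, and the end-of-infusion level is the pre-dose level plus 1. Then S(14)/S(7) = exp(-7k).

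At a 28-day half-life:
- C1D8 = exp(-7k) = 0.841
- C2D1 = 0.500 + 0.595 + 0.707 + 0.841 = 2.643
- C4D1 = 0.125 + 0.149 + 0.177 + 0.210 + 0.250 + 0.354 + 0.500 + 0.707 = 2.471 (summed before rounding)
- C2D1/C1D8 = 2.643/0.841 = 3.14
- C4D1/C1D8 = 2.471/0.841 = 2.94
- same-interval C4D1 ratio = 2.471/exp(-14k) = 2.471/0.707 = 3.49
- shortfall = 1 - 0.841 = 16%

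**4. Other half-lives.** All rows except 28 days are assumptions.

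| Half-life (days) | C2D1/C1D8 | C4D1/C1D8 | Same-interval C4D1 | SAP ratio low by | End of infusion, C2D1 then C4D1 |
|---|---|---|---|---|---|
| 14 | 2.56 | 1.49 | 2.10 | 29% | 2.81, 2.05 |
| 21 | 2.92 | 2.27 | 2.86 | 21% | 3.32, 2.80 |
| 28 | 3.14 | 2.94 | 3.49 | 16% | 3.64, 3.47 |
| 35 | 3.29 | 3.49 | 4.01 | 13% | 3.86, 4.04 |
| 40 | 3.37 | 3.83 | 4.32 | 11% | 3.98, 4.39 |

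**5. Trend from C2D1 to C4D1.** The SAP trough ratio falls only for half-lives below about 31 days. Below about 22 days the same-interval ratio falls too. At 28 days the pre-dose and end-of-infusion levels both drop by 0.17 of a single dose's peak, and C4D1/C2D15, two 14-day troughs, is 2.471/2.576 = 0.96. Relative to the first week, average concentration at 28 days is 3.14 over the last week of Cycle 1 and 3.22 from C3D15 to C4D1. At that half-life the SAP trough pair falls, the same-interval pair rises and the average hardly moves.

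**The case against.** The strongest reply has four parts.

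- **C1D8 is the only trough observed after a single dose.** The second infusion is on Day 8, so a 14-day single-dose trough never exists in the data, and the 16% is measured against a modelled quantity. This stands. It limits the remedy but does not make the two intervals equal.
- **The SAP names the visits openly and plans other summaries.** It has end-of-infusion ratios without this mismatch, concentrations by sampling time, and a population-PK model that may already report Cycle 4 accumulation. This reduces the consequence, but nothing in SAP 2.4.6 qualifies the C4D1 trough ratio.
- **The size rests on assumptions.** The model is not in the documents, and the 28-day figure comes from a contraception rationale. This also stands. The direction is secure; the percentage is indicative.
- **The reporting point may have passed.** SAP Table 10 places PK at the primary PFS analysis only, and SAP version 3 follows a protocol amendment issued after that analysis. This affects where the correction goes, not whether the ratio is mixed.

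A reader might go further and infer that the ratios will falsely show accumulation or exposure falling after Cycle 2, with only the interval having changed. The documents do not support that. Both ratios share the C1D8 denominator, so any drop between them is a drop in measured pre-dose concentration. The dose stays at 10 mg/kg while its frequency halves, and the end-of-infusion ratios also fall at 28 days. With a half-life of 35 days the SAP ratio would rise.

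**Conclusion.** The point holds in a limited form. C4D1/C1D8 as defined in SAP 2.4.6 mixes a 14-day and a 7-day interval and lies below a same-interval ratio by exp(-7k). The shortfall is about 16% at the protocol's 28-day half-life and about 11% to 29% for assumed half-lives of 40 to 14 days, all under a linear one-compartment model. Non-linear or time-varying clearance would change these percentages. C2D1/C1D8 is a matched comparison and is unaffected.

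The two trough ratios should not be read side by side as a trend in accumulation. Equally, a fall between them should not be dismissed as an artefact, since part of it would reflect the lower dosing frequency. The importance is minor.

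**What to change.** In SAP 2.4.6:
- Keep C2D1/C1D8 and both end-of-infusion ratios.
- Take trough accumulation at Cycle 4 from the planned individual population-PK estimates, as the 14-day trough over the predicted 14-day level after a single dose.
- If C4D1/C1D8 is still reported, label it as not adjusted for the change from weekly to two-weekly dosing.
- C4D1/C2D15 may be added as a check of approach to steady state, using samples already in the PK flow chart. It compares two multiple-dose troughs and should not be called an accumulation ratio.

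The cost is a line or two of SAP text and no new sample. If the PK tables have already been produced, a footnote there and a sentence in the PK report serve the same purpose. The drawback is that the matched reference is model-based and depends on a population-PK plan held in a separate document.
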